## CHAPTER 1 INTRODUCTION

127

### 1.1 Introduction and Rationale

128

#### 1.1.1 Hormone Responses during Hypoglycemia

129 Hypoglycemia is a life-threatening side effect of intensive insulin therapy in patients with Type 1  
130 diabetes (1, 2) This is especially the case in children and adolescents and it is observed as an acute  
131 problem in very young children.(3) In all aspects of the daily care of children with diabetes the  
132 degree of burden is higher in younger children than in older children, adolescents or adults. The  
133 recent increase in the number of very young children diagnosed with diabetes and the ever-present  
134 dilemma between good glucose control and the risk of hypoglycemia in these children have brought  
135 to light the problem of detection of hypoglycemia and the factors affecting the response to  
136 hypoglycemia in these children.(4) The use of new methods of continuous glucose monitoring has  
137 revealed multiple instances of asymptomatic hypoglycemia both nocturnal and during awakening.  
138 This phenomenon, although present in all children and adolescents, is much more frequent in  
139 younger children. As a result, these very young children have a higher frequency of seizures,  
140 nocturnal or otherwise, which may result in possible neurocognitive deficits at a later age.(5)

141  
142 In children with Type 1 diabetes, the phenomena associated with hypoglycemia such as counter  
143 regulatory hormone responses and autonomic responses to hypoglycemia have not been evaluated  
144 as extensively as in adults.(6) In adults, extensive studies have addressed the effect of diabetes and  
145 other factors on counter-regulatory hormone and symptomatic responses to hypoglycemia.(1, 2)  
146 These studies were made possible by the development of insulin infusion protocols and the  
147 hypoglycemic clamp technique to provide a controlled, safe, and reproducible hypoglycemic  
148 stimulus in different groups of subjects or in the same subjects under different conditions. Using  
149 these techniques, it has been shown that long diabetes duration, intensive insulin treatment,  
150 exercise, sleep and antecedent hypoglycemia reduce adrenomedullary (plasma epinephrine), central  
151 sympathetic (plasma norepinephrine), and symptomatic response to hypoglycemia.(7) In most of  
152 these studies, reductions in sympathetic responses were related to a lowering of the plasma glucose  
153 level that was required to stimulate a rise in plasma catecholamine levels. In contrast, plasma  
154 epinephrine responses to hypoglycemia are increased in older children and adolescents with or  
155 without diabetes compared to corresponding responses in adults with or without diabetes (8) due to  
156 an upward shift in the plasma glucose threshold for release of catecholamines.(9)

157  
158 In addition, studies in adults with Type 1 diabetes have addressed the effect of duration of diabetes  
159 as well as recent antecedent hypoglycemia on glucose counter-regulatory hormones response and  
160 autonomic response manifested as hypoglycemic symptoms.(10) In a number of elegant studies in  
161 adults with diabetes and normal subjects, several groups have experimentally induced  
162 hypoglycemia and measured the responses to hypoglycemia on days following normoglycemia or  
163 following another episode of hypoglycemia. There is consensus that antecedent hypoglycemia  
164 reduces adrenomedullary epinephrine, sympathetic neural norepinephrine, neurogenic symptoms  
165 and glucagon on subsequent hypoglycemia, whereas Growth hormone and cortisol responses have  
166 been found to be unaltered in normal subjects.(11, 12) In addition exercise and the counter-  
167 regulatory hormone response to antecedent exercise have been shown to reduce epinephrine and  
168 growth hormone response to subsequent (next few days) hypoglycemia while cortisol,  
169 norepinephrine, glucagon and neurogenic symptoms were not affected.(13)

170  
171 The ability to detect hypoglycemia depends on several systems that encompass the spectrum of  
172 neurocognitive maturity and level of hormonal counter-regulatory response maturity.(14) It is not

173 known if young children with diabetes have an intact counter-regulatory hormone response. In  
174 newborn infants it has been shown that a robust counter-regulatory hormone response to  
175 hypoglycemia can be elicited but sympathomimetic symptoms are usually lacking.(15)

176  
177 The question of whether autonomic symptoms and counter-regulatory hormone response to  
178 hypoglycemia is dependent on age or developmental stage or is impaired by diabetes duration or  
179 frequency of antecedent hypoglycemia in children has not been examined adequately. Children  
180 have several physiologic factors that may affect response to hypoglycemia, such as developmental  
181 and maturity stage as well as hormonal and pubertal stage. Studies to date that have tried to address  
182 this issue in children have concluded that there was no difference noted in the different stages of  
183 development but the youngest children included in this study were 9 years old.(16) In addition in a  
184 different study examining the counter regulatory response to nocturnal hypoglycemia in prepubertal  
185 children, a lower hormonal response was only partially responsible for the prolonged nocturnal  
186 hypoglycemia observed in these 6-13 year old children.(17)

187  
188 In comparison to children without diabetes, counter regulatory responses were lower in children  
189 with diabetes (mean age of 14 years for both groups) but autonomic symptom recognition was  
190 similar. Despite the lower counter regulatory hormone response in children with diabetes, the  
191 glycemic threshold for adrenaline to increase higher than 2 SD above basal was  $63 \pm 3$  mg/dL in  
192 these children.(18) In adolescent children with diabetes epinephrine responses during sleep were  
193 lower than in normal children (19) but in a controlled hypoglycemia setting with an insulin clamp,  
194 children with and without diabetes had higher epinephrine responses than adults.(8) In a study of  
195 insulin induced hypoglycemia (glucose  $<60$ mg/dL) adolescents with diabetes had a lesser  
196 catecholamine response than matched controls and this response was even lower in intensively  
197 treated youth with diabetes. Furthermore this study demonstrated that nadir glucose level is the  
198 important determinant of counter regulatory hormone response and not the rate of glucose decrease  
199 to the nadir glucose level.(20)

200  
201 Despite the clinical importance of avoiding hypoglycemia in very young children with T1DM, no  
202 studies have examined and compared the adequacy of counterregulatory hormone defense  
203 mechanisms in very young versus older children with T1DM. This may be related to practical  
204 problems with carrying complex insulin infusion and glucose clamping procedures in infants and  
205 toddlers. Nevertheless, it is likely that the ability to detect and respond to hypoglycemia is reduced  
206 in very young patients. Moreover, parents of young children with T1DM often anecdotally report  
207 absence of any signs and symptoms of hypoglycemia, even in the face of plasma glucose levels  $<$   
208  $30$  mg/dl. In a study of six preschool age children, insulin induced hypoglycemia resulted in normal  
209 epinephrine, norepinephrine and growth hormone response but no glucagon response.(21) In this  
210 study intravenous insulin lowered glucose levels from  $80$  to  $40$ mg/dL over one hour and counter  
211 regulatory hormone levels were only measured at baseline and at nadir glucose.

212  
213 The present study is being undertaken to compare counterregulatory hormone responses to a mild  
214 and gradual reduction in plasma glucose in young children with T1DM versus responses in  
215 adolescents. The studies will be performed under the close supervision of the professional staff of  
216 each DirecNet center and frequent bedside monitoring of plasma glucose concentrations will ensure  
217 that clinically significant hypoglycemia is prevented from developing. All subjects will be admitted  
218 to the CRC and have an IV line for blood sampling inserted on the evening prior to study to reduce  
219 stress on the morning of the study. The study procedure will be simplified and made less invasive in  
220 comparison to a clamp or standard insulin infusion study (i.e. only the one IV for blood sampling  
221 will be needed) by limiting enrollment to insulin pump-treated subjects who will have their basal  
222 rates modestly increased to produce the hypoglycemic stimulus. Monsod and colleagues used the

223 same procedure of increasing the basal insulin infusion dose to induce a gradual fall in plasma  
224 glucose in youth with type 1 diabetes in a study that compared the ability of injections of glucagon  
225 and epinephrine to treat mild hypoglycemia. (22) It is particularly important to note that once the  
226 blood glucose level falls below 60 mg/dl, a blood sample will be obtained and hypoglycemia will  
227 then be immediately corrected by intravenous administration of exogenous glucose. In our recent  
228 DirecNet study,(23) ~25% of children and adolescents had plasma glucose levels below 60 mg/dl  
229 during a typical night and this rose to ~50% of subjects when there was antecedent exercise in the  
230 late afternoon. Moreover, the frequency of mild as well as severe hypoglycemia is substantially  
231 higher in pre-school children than in children and adolescents. This safe and rigorously designed  
232 study will provide important new information regarding the role of inadequate counter-regulation  
233 on the increased risk of hypoglycemia in very young children with T1DM.

234

### 235 **1.1.2 Evaluation of Continuous Glucose Monitoring Systems**

236 Real-time continuous glucose sensing systems offer the potential to markedly lower the risk of  
237 hypoglycemia in youth with T1DM. However, the DirecNet inpatient accuracy study demonstrated  
238 that the first generation of these devices was inaccurate when blood glucose was lowered to less  
239 than 70 mg/dl. In that study, children with T1DM between 3-17 years of age were admitted to the  
240 CRC for approximately 26 hours during which they wore 1-2 Medtronic MiniMed CGMS and 1-2  
241 Cygnus GlucoWatch G2 Biographer continuous glucose monitors. In every subject in that study,  
242 blood samples were obtained every 30-60 minutes from an indwelling intravenous catheter for  
243 measurement of reference plasma glucose levels in the DirecNet Central Laboratory. The Guardian-  
244 RT continuous glucose monitoring systems is a real-time continuous glucose monitor that has  
245 considerable promise for use in children with diabetes. Therefore, a secondary aim of this study is  
246 to obtain very important data regarding the accuracy of this system during hypoglycemia in young  
247 children, as well as adolescents.

248

249 The Guardian-RT has been approved by the FDA for detecting trends and tracking patterns in adults  
250 (18 and older) and are indicated for adjunctive rather than replacement of standard home glucose  
251 monitoring devices. The sensor has been approved by the FDA for use for up to 72 hours but can  
252 function for a longer period of time.

253

#### 254 **1.1.2.1 Background on the Guardian-RT**

255 The Guardian-RT was developed and is distributed by Medtronic Minimed. This sensor uses a  
256 glucose oxidase based electrochemical sensor which generates 2 electrons for each glucose  
257 molecule oxidized. The current generated from measuring glucose is called the ISIG (Input  
258 SIGnal). The Guardian-RT system is designed to measure blood glucose levels in a range of 40-400  
259 mg/dl. The sensor is inserted subcutaneously and measures interstitial glucose. When functioning  
260 properly, the Guardian-RT acquires glucose values every 10 seconds and these values are averaged  
261 in the monitor to provide a reading every 5 minutes (or 288 readings a day) which is transmitted  
262 wirelessly to a receiver that can be kept up to 6 feet from the transmitter. Each sensor is designed to  
263 measure readings for up to 72 hours.

264

265 The Guardian-RT has alarms for hypoglycemia and hyperglycemia that can be adjusted by the user.  
266 Subjects can enter events, such as when they took insulin, ate, or exercised. The sensor requires at  
267 least 2 capillary glucose readings each day (every 12 hours) to validate sensor function and allow  
268 for development of a calibration equation. These calibration measurements are performed with a  
269 home glucose meter, and calibration is dependent upon the subject entering glucose values correctly  
270 into the sensor.

271

## 272 **1.2 Study Objectives**

273 The primary objective of this study will be to compare the glucose level at which counter-regulatory  
274 hormone responses occur during hypoglycemia in young children with diabetes, with the glucose  
275 level counter regulatory hormone responses that occur in older children with diabetes. We  
276 hypothesize that the children in the younger age group will not have a counterregulatory response  
277 until a lower glucose level is reached compared with children in the older age group.

278  
279 Secondary objectives will be:

- 280  
281 1 To assess signs and symptoms at different glucose levels of hypoglycemia in younger children  
282 and compare those with the older children. Furthermore, symptoms will be compared to counter  
283 regulatory hormone levels in the two age groups. Symptoms will be assessed using physiologic  
284 data and using an age-appropriate questionnaire that would be completed during the test by the  
285 subject (where appropriate) and by a parent.
- 286  
287 2 To assess whether there is a difference in counter-regulatory hormone response in each age  
288 group, among those who had at least 2-3 episodes of hypoglycemia per day or night prior to the  
289 study compared with those who had an occasional or no episodes of hypoglycemia prior to the  
290 test. Subjects will wear a Guardian RT for 6 days ( $\pm 1$  day) prior to the test to assess episodes of  
291 hypoglycemia.
- 292  
293 3 To examine the accuracy of the Guardian-RT during hypoglycemia in children with type 1  
294 diabetes.

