### 7.1 Sample Size

Jones et al. (9) measured hormone levels in children with type 1 diabetes during induced hypoglycemia. The standard deviation (calculated by multiplying their reported standard error by the square root of the sample size and dividing by 5.46 to convert to pg/mL) for epinephrine was 306 pg/mL. With this standard deviation and a two-tailed test with type I error rate of 5%, a sample size of 50 subjects (25 in each age group) will give approximately 92% power to detect a mean difference of 300 pg/mL between the two age groups.

After N=30 subjects have completed the subcutaneous insulin infusion test an interim analysis will be performed to re-evaluate the sample size calculation above. The standard error for the age effect from the ANCOVA model for epinephrine described in section 7.2.1.1 will be calculated using the outcome data from the first 30 subjects. This will be used to update the calculation above to obtain the sample size necessary to detect a mean difference of 300 pg/mL with 90% power. Results will be presented to the DirecNet DSMB to determine whether the study should be stopped for either efficacy/futility or whether recruitment should continue to the newly calculated sample size (up to a maximum of 50 total subjects).

To avoid inflating the type I error rate with this interim analysis, the following stopping guidelines will be recommended: If N=30 subjects provides  $\geq 80\%$  power using the updated variance estimate or if N=50 would only increase this power by  $< 5\%$ , then no additional subjects will be recruited and statistical analysis will proceed without adjustment for alpha spending. Otherwise, Pocock's test will be used to determine whether to stop at N=30 or continue recruitment to the newly calculated sample size (up to a maximum of 50 total subjects). If conditional power based on the age effect observed so far is less than 30% then stopping for futility will be recommended.

Based on the results a pilot study of the FreeStyle Navigator™ (Abbott Diabetes Care) performed by DirecNet, a sample size of 30-50 subjects will result in approximately 1,800-3,000 sensor-reference pairs giving a 95% confidence interval for the median relative absolute difference no more than  $\pm 1.0\%$ . With this sample size the half width of the 95% confidence interval for the median difference will be approximately  $\pm 5-6$  mg/dL.

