### 7.2 Analysis Plan

#### 7.2.1 Counterregulatory Responses during Insulin-induced Hypoglycemia

##### 7.2.1.1 Hormone Concentrations

Boxplots will be used to summarize the distribution of hormone levels separately for the two age groups by glucose level. An analysis of covariance model (ANCOVA) will be fit separately for each hormone with the change from baseline to peak during the subcutaneous insulin infusion test as the dependent variable. The model will include a term for age group (3-<7 vs. 12-<18) with baseline hormone concentration as the covariate.

A repeated measures regression model will also be fit treating each hormone measurement as a separate observation (instead of just using the peak value as above). Either an autoregressive or Toeplitz structure will be used to model the covariance pattern. Residual values will be checked for

918 approximate normality. If the distribution is highly skewed a transformation may be used.  
919 Suspected outliers will either be truncated or excluded.

920  
921 Additional exploratory models will be fit to assess possible associations of counterregulatory  
922 responses with the following covariates:

- 923 • age as continuous
- 924 • HbA1c
- 925 • gender
- 926 • BMI percentile
- 927 • clinical center
- 928 • glycemic indices as measured by the Guardian RT during home use prior to the  
929 subcutaneous insulin infusion test (see section 7.2.2.1)

930  
931 Continuous covariates will be modeled as linear in the dependent variable or divided into categories  
932 if significant non-linearity is detected. The number of hypoglycemic episodes per 24 hours  
933 measured by the Guardian RT will also be categorized as  $<2.0$  vs.  $2.0-<3.0$  vs.  $\geq 3.0$ .

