### 934 **7.2.1.2 Glucose Level Triggering a Counterregulatory Response**

936 For each hormone, the glucose level at which a counterregulatory response was observed will be  
937 treated as a secondary outcome. A response will be defined as the first glucose level at which there  
938 was a sustained increase of the hormone concentration at least 3 standard deviations above baseline.  
939 If no such increase is observed, then the subject will be deemed not to have responded to  
940 hypoglycemia.

941  
942 If the outcome values are not skewed a regression model with a normal distribution and interval  
943 censoring will be fit to the data using maximum likelihood. Age group and the baseline hormone  
944 value will be included as independent variables. If significant non-linearity is detected with the  
945 baseline hormone, it will be divided into categories and treated as a discrete variable. If the values  
946 show a skewed distribution then an alternate distribution such as a Weibull or lognormal will be fit  
947 by maximum likelihood. If no distribution can be found to give a good fit to the data, then a semi-  
948 parametric proportional hazards regression will be fit.

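### The primary objective is the glucose level that triggers a hormone response, but the plan makes that outcome secondary and bases its power and interim rules on epinephrine concentration

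*Protocol*

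**What the plan says.** Four parts of the protocol bear on what is primary.

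- **Section 1.2 (objectives):** "The primary objective of this study will be to compare the glucose level at which counter-regulatory" hormone responses occur, in younger versus older children. The hypothesis is that the younger group will not respond "until a lower glucose level is reached compared with children in the older age group". Both are in mg/dL of glucose.
- **Section 7.2.1.2 (triggering glucose level):** for each hormone, this quantity is "treated as a secondary outcome". Its model begins: "If the outcome values are not skewed a regression model with a normal distribution and interval" censoring, with age group and baseline hormone as independent variables.
- **Section 7.1 (sample size):** "a sample size of 50 subjects (25 in each age group) will give approximately 92% power to detect a mean difference of 300 pg/mL" in epinephrine, using an SD of 306 pg/mL and a two-sided 5% test. After 30 subjects, the standard error of the age effect from the epinephrine ANCOVA is used to recalculate the sample size. The Pocock test and the futility rule follow in the same section.
- **Section 7.2.1.1 (hormone concentrations):** "An analysis of covariance model (ANCOVA) will be fit separately for each hormone with the change from baseline to peak" as the dependent variable. A repeated measures model is fitted as well. Neither is called primary, and no hormone is singled out.

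Section 3.3.2 defers the choice of which stored samples to process until the primary outcome is known, but the protocol never defines that outcome. Chapter 7 says the later analysis plan will replace section 7.2; it does not say the same of 1.2 or 7.1.

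**The concern.** One quantity is the subject of the primary objective in one section and a secondary outcome in another. The stated power and every rule that can end recruitment belong to a different quantity, on a different scale, with a different model.

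Two things are at stake. A reader who takes 92% as the trial's power for its primary objective is misled, because nothing in the document supports that figure in mg/dL. Recruitment could also stop at 30 subjects because the epinephrine comparison has at least 80% power, because going to 50 would add less than 5 points, because the Pocock boundary is crossed, or because conditional power is below 30%. In each case the outcome named in the primary objective would have played no part in the decision.

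**Working it through.** **1. Reproduce the plan's figure.** Inputs from section 7.1: difference 300 pg/mL, SD 306 pg/mL, 25 per group, two-sided 5%.

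- Noncentrality = 300 / (306 × √(2/25)) = 300 / 86.55 = 3.47.
- Two-sample t-test, 48 df, critical value 2.01: power 92.5%.
- Normal approximation: Φ(3.47 − 1.96) = 93.4%.

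The stated 92% is correct for epinephrine. It corresponds to a difference of 300/306 = 0.98 SD.

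**2. Try to carry it to the primary objective.** This needs an SD and a target difference for the triggering glucose level. Section 7.1 gives neither. The nearest figure is in section 1.1.1: an adrenaline threshold of 63 ± 3 mg/dL in children with diabetes, from a cited study with a mean age of 14. It is not stated whether the ±3 is an SD or a standard error, and the rise there was 2 SD above basal, whereas section 7.2.1.2 uses 3. So the SD has to be assumed and a range shown.

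**3. Power if each child's triggering level were known exactly** (t-test, 25 per group, assumed SDs):

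| SD (mg/dL) | Power, 5 mg/dL | Power, 10 mg/dL | Difference detectable with 92% power |
|---|---|---|---|
| 6 | 82% | >99% | 5.8 mg/dL |
| 8 | 58% | 99% | 7.8 mg/dL |
| 10 | 41% | 93% | 9.7 mg/dL |
| 12 | 30% | 82% | 11.7 mg/dL |
| 15 | 21% | 64% | 14.6 mg/dL |

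**4. Power under the planned sampling.** Hormones are sampled when glucose is below 90, 80, 70 and 60 mg/dL, so the level is known only to an interval, and levels below 60 are not observed. Assumptions: normal triggering levels, means 63 (older) and 58 (younger), equal SDs, age group as the only term (the baseline hormone covariate in section 7.2.1.2 is omitted), and a likelihood-ratio test at 5%. The ranges come from repeated simulations of 300 to 1,000 trials each.

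| Assumed SD (mg/dL) | Simulated power, 25 per group |
|---|---|
| 3 | over 99% |
| 5 | 84-87% |
| 6 | 69-71% |
| 8 | 43-56% |
| 10 | 35-45% |
| 15 | 16-20% |

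The simulation standard error near 50% with 300 trials is √(0.5 × 0.5 / 300) = 2.9 points, so the middle rows are approximate. With 15 per group, the size if the trial stops at 30, the same scenario gives about 32-35% at SD 8 and 23-27% at SD 10. A larger difference does much better: 10 mg/dL at SD 10 gives about 85-91% with 25 per group.

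**5. Reading.** Depending on an SD the protocol does not state, power for a 5 mg/dL difference could be well above or far below 92%. The figure cannot be transferred in either direction.

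**The case against.** **Peak response and threshold are related.** Section 1.1.1 links reduced sympathetic responses to a lower glucose threshold, and larger epinephrine responses in youth to a higher one. Every test has the same glucose endpoint, so a child who responds later would tend to show a smaller rise to peak. This stands as a reason to measure epinephrine. It does not make the two outcomes one: a child may respond at the same glucose with a smaller peak, and the protocol gives each its own model.

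**Section 7.1 does single out one test.** This also stands. A reader might infer that the trial has no primary test at all. The documents do not support that, since the epinephrine ANCOVA alone drives the re-estimation and stopping rules. The fault is that it is not designated and does not match section 1.2.

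**The analysis plan will settle it.** Only in part. It replaces section 7.2, so the mismatch between 1.2 and 7.1 would remain.

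**Two further inferences go too far.** A reader might conclude that the triggering-level analysis is underpowered. The document gives no power calculation for it, which is not evidence of low power, and at SDs of about 5 mg/dL or less power is good even for a 5 mg/dL difference. A reader might also infer that testing five hormones inflates the error rate of the primary claim. The protocol nowhere says that success on any one hormone counts, section 7.1 attaches the 5% error rate to epinephrine only, and the ranking of the other hormones can be left to the analysis plan.

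**Conclusion.** The mismatch is in the protocol's own text and needs no assumption: section 1.2 names one primary quantity, section 7.2.1.2 ranks it as secondary, and section 7.1 powers and monitors another. It should be corrected before the plan is used, because stopping decisions depend on it.

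The 92% is right for a 300 pg/mL epinephrine difference and has no standing for the primary objective. The power for that objective is unknown. The range from over 99% down to 16-20% rests on an assumed difference of 5 mg/dL, assumed SDs of 3-15 mg/dL and the simulation model above. It measures how much the missing inputs matter and does not estimate the trial's actual power.

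**What to change.** Name one primary outcome, one hormone (epinephrine) and one test, in the same terms in sections 1.2, 7.1 and 7.2. Either route is coherent, and the choice is the sponsor's.

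- **(a) Epinephrine change as primary.** Designate the ANCOVA on change from baseline to peak as the primary analysis, reword the primary objective and hypothesis to match, and keep the triggering glucose level as key secondary. Section 7.1 and the interim rules can stay on this outcome. Cost: wording only, at the price of changing the stated hypothesis.
- **(b) Triggering glucose level as primary.** Make the section 7.2.1.2 analysis for epinephrine the primary analysis and stop presenting 92% as the trial's power. State the power or detectable difference at N=30 to 50 over a stated SD range, allowing for interval censoring and for children who have not responded by the time the test ends. Base the re-estimation, Pocock and futility rules on this analysis. Cost: a short simulation, and possibly a less favourable stated power at the N=50 cap. Extra subjects come into question only if the sponsor wants to keep a 90% target and the assumed SD does not allow it.

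Under either route, the reference to the primary outcome in section 3.3.2 then has a defined meaning.
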